1.1. Primary

- 1.1.1. To provide access to treatment with investigational convalescent plasma to inpatients with documented COVID-19 infection
- 1.1.2. To measure NAb titers in an aliquot of the CP administered, to measure the volume of CP administered, and determine whether there is a correlation between the NAb dose (in NAb units/kg body weight, where a unit is the reciprocal of the endpoint NAb titer in the CP multiplied by the volume in ml) and change or lack of change when comparing pre-treatment and day one NAb titers.

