In light of limited availability of CP and the urgent need for promising therapies for COVID-19, it will not be initially feasible to measure NAb titers in the convalescent plasma (CP) prior to plasma administration or to adjust the volume of CP to be administered based on NAb titer in the CP or the body weight or plasma volume of the recipient. However, while this study does not involve administration of plasma with known NAb titer, information gained from the current study may help inform dosing in the future, including in potential dosing modifications that could be submitted via a protocol modification.

PROTOCOL TITLE: Open, non-comparative pilot study to provide access to treatment with investigational convalescent plasma and measure antibody levels in patients hospitalized with COVID-19

The correlation between the levels or titers of neutralizing antibodies after CP transfusion and viral shedding has not been sufficiently explored. Are certain levels of neutralizing antibodies associated with viral clearance? In the study by Duan et al., the viral load was undetectable after transfusion in seven patients who had previous viremia (Duan et al.) We propose to monitor viral shedding in respiratory secretions after CP transfusion. The presence of the virus is relevant for transmission, especially in the hospital setting.

3. Study Design

This is an open label pilot study designed to provide access to treatment with investigational convalescent plasma and assess the relationship between NAb titers in the investigational convalescent plasma compared to changes in NAb levels in the recipient in hospitalized patients with COVID-19.

4. Inclusion and Exclusion Criteria

Inclusion Criteria for Enrollment

1. Patients must be 18 years of age or older.
2. Hospitalized with COVID-19 respiratory symptoms and confirmation via COVID-19 SARS-CoV-2 RT-PCR testing. If COVID-19 test results are pending or done at enrolment, test results must be positive prior to administration of convalescent plasma.
3. Patient (or legally authorized representative, LAR) is willing and able to provide written informed consent and comply with all protocol requirements.
4. For patients unable to consent, consent by the legally authorized representative (LAR) may be obtained by phone.

Exclusion Criteria

1. Female subjects with positive pregnancy test or breastfeeding.
2. Receipt of pooled immunoglobulin in past 30 days.

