3. Contraindication to transfusion or history of prior severe allergic reactions to transfused blood products
4. On ECMO or in refractory shock at entry

5. Number of Subjects

This pilot aims to explore safety and measure antibody levels in patients treated with CP. We aim to enroll 30 subjects to ensure the estimate of *neutralizing antibodies* to be within 20% margin of error.

PROTOCOL TITLE: Open, non-comparative pilot study to provide access to treatment with investigational convalescent plasma and measure antibody levels in patients hospitalized with COVID-19

6. Study Timelines

Hospitalized patients will be enrolled as soon as their COVID-19 diagnosis is confirmed, using approved diagnostic methods, and will be followed until hospital discharge or death. Patient enrollment will start immediately after IRB approval. We anticipate a 3-month enrollment. The study will continue for another 24-months after the last enrollment during which we will be able to process and analyze data, and disseminate findings.

7. Study Endpoints

7.1. Primary endpoint:

- 7.1.1. Titers of SARS-CoV-2 neutralizing antibodies measured by focus reduction neutralization test (FRNT) at days 0 (pre-transfusion), 1, 3, 7 and 14 days of CP transfusion.

- 7.1.2. Availability of convalescent plasma

7.2. Secondary endpoints:

Clinical outcomes:

- 7.2.1 Serious adverse events
- 7.2.2 SARCoV-2 viral shedding in nasopharyngeal samples determined by RT-PCR
- 7.2.3 Genomic variations of SARS-CoV-2 before and after CP transfusion
- 7.2.4 Transfer to ICU
- 7.2.5 Type and duration of respiratory support (and other ICU support including ECMO, CRRT) in ICU
- 7.2.6 Cardio-circulatory arrest (at any time)
- 7.2.7 ICU mortality and LOS
- 7.2.8 Hospital mortality and LOS
- 7.2.9 Ventilator-free days
- 7.2.10 In hospital mortality
- 7.2.11 Titer of other functions of antibodies, including antibody-dependent cell-mediated and complement-dependent cytotoxicity

7.3. Safety Endpoints:

- 7.3.1 Rapid deterioration of respiratory or clinical status on transfusion of SARS-CoV-2 convalescent plasma.
- 7.3.2 Cumulative incidence of serious adverse events during the study period: febrile non-hemolytic transfusion reaction, allergic transfusion reaction, transfusion related acute lung injury (TRALI), transfusion associated circulatory overload (TACO),

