PROTOCOL TITLE: Open, non-comparative pilot study to provide access to treatment with investigational convalescent plasma and measure antibody levels in patients hospitalized with COVID-19

- 12.1. Potential subjects will be identified by reviewing the registry of +SARSCoV2 RTPCR testing (at TRICORE laboratory) in hospitalized patients.
- 12.2. Eligibility of the potential study participants will be identified by their treating providers (Hospital Medicine and Intensive Care Unit). The treating providers will notify representatives of the research team. Members of the research team will verify the eligibility of the potential subjects and will obtain informed consent from them or their LAR.
- 12.3. Once the participant or their LAR gives their written informed consent, the research team will notify the treating provider so they can place the medical order for the investigational products. If LAR consented via phone, a copy of the consent form will be mailed to LAR.
- 12.4. The protocol specific activities are detailed in Table 1
- 12.5. Treatment

Subjects will receive the convalescent plasma.

Study drug: The investigational product is anti-SARS-CoV-2 convalescent plasma obtained from former patients identified as having recovered from COVID-19 and obtained by Vitalant from local and national donors following national blood donation guidelines. These donors will be cleared for blood donation like any other volunteer blood donor and samples will have been screened for transfusion-transmitted infections (e.g. HIV, HBV, HCV, WNV, HTLV-I/II, T. cruzi, ZIKV) both through the use of the uniform donor questionnaire and FDA mandated blood donor screening tests. This single-donor plasma product will have been collected using apheresis technology and in accordance with standard FDA and blood bank protocols.

A 1ml of aliquot of anti-SARS-CoV-2 plasma will be saved for NAb titer measurement by FRNT (as mention in section 8.) in the CGH laboratory and the total volume of plasma administration will be recorded.

 - 12.5.1. Study subjects will receive 1 unit (200mL) of SARS-CoV-2 convalescent plasma collected from a single donor who recovered from COVID-19.

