Our primary endpoint for statistical analysis is changes in NAb titers at day 1, 3, 7, and 14 from the entry level (day 0). Our primary hypothesis is that NAb titers will increase post-transfusion in positive correlation with transfused volume of convalescent plasma when adjusted for NAb titer in the convalescent plasma. We will use repeated measurements analysis of variance (ANOVA) or analysis of covariance (ANCOVA) when controlling for other factors (e.g. use of hydroxychloroquine) for initial exploration of the association with the transfusion volume of convalescent plasma. A more advanced approach is to use nonlinear regression models with random effects to characterize the trajectory of NAb titers over the course of 14 days. This latter approach can effectively characterize individual-specific trajectory in NAb titers in relation to convalescent plasma, and at the same time quantify between-patients variation, thereby improving statistical power. This mixed-effects nonlinear regression modeling approach is also capable of adjusting for other factors as appropriate (e.g. patient age). We will also conduct post-hoc analysis of change in NAb titers from day 0 to a specific day (day 1, 3, 7, or 14) post transfusion of convalescent plasma when appropriate. Better understanding and better characterization of the relationship between NAb titers and amount of convalescent plasma transfusion adjusted for NAb titer in the convalescent plasma will inform standardized dosage for future study.

In the absence of a comparison group, we will use descriptive statistics to report other parameters of interest (e.g. secondary outcomes), including the use of mean (SD), frequency (%) and their confidence interval. When appropriate, we will also report association between a parameter of interest and a factor of clinical relevance (e.g. duration of shading and underlying comorbidities, NAb titers at a specific post-transfusion day and underlying comorbidities, NAb titers at a specific post-transfusion day and secondary outcomes such as transfer to ICU or hospital death). This analysis will utilize odds ratio and Fisher's test for dichotomous variables, and Wilcoxon test a continuous variable.

We will conduct interim analysis after the first 10 patients complete the study. Based on the interim analysis results we may consider submitting a protocol amendment requesting adjustment our patient recruitment or CP dosing.

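### The primary analysis is defined inconsistently: the objective relates NAb units/kg to the day-1 change, while 13.2 uses four days, plasma volume adjusted for titre, and two models with neither named primary

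*Combined protocol and SAP*

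**What the plan says.** **Day.** Objective 1.1.2, listed under the primary objectives, asks whether NAb dose in units per kg correlates with "change or lack of change when comparing pre-treatment and day one NAb titers". Section 13.1.1 repeats this and adds units/BSA and units/plasma volume as alternative scales. Section 7.1.1 makes the primary endpoint the titres themselves, "measured by focus reduction neutralization test (FRNT) at days 0 (pre-transfusion), 1, 3, 7 and 14 days of CP transfusion". Section 7.1.2 adds a second, non-statistical primary endpoint, "Availability of convalescent plasma". Section 13.2 then states: "Our primary endpoint for statistical analysis is changes in NAb titers at day 1, 3, 7, and 14 from the entry level (day 0"). Later in the same section: "We will also conduct post-hoc analysis of change in NAb titers from day 0 to a specific day (day 1, 3, 7, or 14").

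**Predictor.** The primary hypothesis in 13.2 is that titres rise "in positive correlation with transfused volume of convalescent plasma when adjusted for NAb titer in the convalescent plasma". Body weight does not appear. Section 12.5.1 says: "Study subjects will receive 1 unit (200mL) of SARS-CoV-2 convalescent plasma collected from a single donor". The Background explains that it is not initially feasible "to adjust the volume of CP to be administered based on NAb titer in the CP or the body weight".

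**Model.** Section 13.2 offers repeated-measures ANOVA or ANCOVA as a first, exploratory look and a nonlinear mixed-effects model as a refinement. Neither is designated primary.

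**Multiplicity.** Section 13.2 promises a False Discovery Rate adjustment but lists no family of tests and no level. It also says that the analysis centres on the primary outcome and the primary hypothesis, which presupposes one of each.

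**The concern.** A reader cannot tell from the plan which test is the primary result. The contrast that is primary in 1.1.2 (day 0 to day 1) appears in 13.2 only as one of four days, and again among single-day analyses labelled post-hoc. The exposure differs between the two sections, and the model is left open.

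This matters for two reasons. First, the study is open-label, and 14.7 has a preliminary endpoint analysis shown to the investigators after 10 patients, so the day, predictor and model could be settled after data are seen. Second, the choice of predictor is not neutral. If transfused volume is the regressor and titre a covariate, a fixed unit leaves almost nothing to estimate. Section 13.2 says that the result is meant to inform dosing in a future study, so the dose-response analysis should be identifiable and fixed in advance.

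**Working it through.** **What the plan provides.** N = 30, planned volume 200 mL, and the definition of NAb units (reciprocal titre times mL). The only precision figure is a 20% margin of error in section 5. It cannot be reproduced, because no SD, scale or confidence level is given. For a mean with a 95% interval it would need a CV of 0.20 × √30 / 1.96 = 0.56. The plan gives no power figure for the primary hypothesis, so every spread and effect below is an assumption.

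**1. Power by predictor.** Assumed: log2 plasma titre SD 1.0 to 2.0; recorded volume SD 5 to 20 mL around 200; ln weight SD 0.25; true slope 0.25 log2 per doubling of dose/kg; residual SD 0.7; two-sided 0.05. On the log2 scale the volume SD is SD/200/ln 2 = 0.036 to 0.144, and the weight SD is 0.25/ln 2 = 0.361.

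SE of slope = residual SD / (SDx × √29), with power from the noncentral t distribution.

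| Predictor | SDx | Residual SD | SE | 0.25/SE | Power, formula | Power, simulation |
|---|---|---|---|---|---|---|
| log units/kg | 1.06 to 2.04 | 0.70 | 0.122 to 0.064 | 2.05 to 3.92 | 51% to 97% | 49% to 95% |
| log (volume × titre) | 1.00 to 2.01 | 0.706 | 0.131 to 0.065 | 1.91 to 3.82 | 45% to 96% | 45% to 93% |
| log volume, titre as covariate | 0.036 to 0.144 | 0.706 | 3.63 to 0.91 | 0.07 to 0.28 | 5.1% to 5.8% | 5% to 6% |

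The residual 0.706 is √(0.7² + (0.25 × 0.361)²), because weight is left out of the last two predictors. The formula treats the spread as fixed; simulation lets it vary between samples and comes out slightly lower. Volume supplies only 0.0013/4.13 = 0.03% to 0.0208/1.151 = 1.8% of the variance of log dose/kg. If volume were exactly 200 mL for all, the matrix (intercept, volume, titre) would have rank 2 of 3 and the slope could not be estimated.

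**2. How far volume × titre differs from units/kg.** On log scales the correlation is SD(ln titre) / √(SD(ln titre)² + SD(ln weight)²). For ln titre SD 0.5 to 1.5 and ln weight SD 0.2 to 0.3 it runs from 0.5/√0.34 = 0.86 to 1.5/√2.29 = 0.99. Weight scaling alone is therefore a small conflict.

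**3. Open choice of day, no dose effect.** Four independent tests at 0.05 give 1 − 0.95⁴ = 18.5%. The days are correlated within a patient, so I simulated 30 patients with day loadings 0.1, 0.3, 0.8 and 1.0 on a patient response of SD 1. Residual SD was 0.7, or 0.5 with a shared baseline error of SD 0.5. One fixed day-1 test gives about 5%. The best of four days gives about 14% to 18%. Benjamini-Hochberg over the four listed tests gives about 5%.

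**4. Why day-0 titre belongs in the model.** Under simple dilution of 200 mL into an assumed 3,000 mL of plasma, the post-transfusion titre is (B × 3000 + C × 200)/3200, with B the baseline and C the plasma titre. Raising C from 80 to 1280 adds 2.64, 1.47, 0.57 and 0.17 log2 at B = 10, 40, 160 and 640. The same dose moves the log titre far less when the baseline is high.

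**The case against.** **The hypothesis may mean volume × titre.** Section 13.2 closes by speaking of the amount of plasma adjusted for its titre, which is naturally the NAb unit of 1.1.2 without weight. This stands as an available reading. It removes the power problem, but the day and model conflicts remain, as does the smaller one of weight scaling.

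**Volume may not stay constant.** Administered volume is recorded (12.5), the Background calls adjustment only initially infeasible, and 13.2 allows a dosing amendment after the interim. A reader might infer that the primary hypothesis is untestable outright. The documents support less: it is practically inestimable on the covariate reading while the current plan holds.

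**FDR is planned.** A reader might multiply days by predictors and quote a much larger false-positive rate. That describes an analysis without the promised adjustment, and it depends on pairing units/kg with the covariate reading. What stands is that no family of tests is listed.

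**Post-hoc may mean follow-up contrasts.** After a repeated-measures ANOVA that is common usage. The standing of day 1 is then unclear rather than plainly demoted.

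**Late samples.** A reader might infer that discharge or death will bias the primary result. The documents give no amount of loss, do not say that the ANOVA uses complete cases, and already plan a random-effects model, which can use partial profiles. A two-sample day-1 analysis is not touched by later loss.

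**It is a pilot.** Section 13.2 disclaims power for all analyses. That limits the consequence but does not excuse two definitions of the primary analysis.

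**Conclusion.** The inconsistency is in the text and needs no simulation to establish. Sections 1.1.2 and 13.1.1 use units/kg and day 1; 7.1.1 uses titres at five time points; 13.2 uses changes at four days and volume adjusted for titre; no model is primary. It should be corrected before analysis.

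The size depends on the reading. On the covariate reading the stated hypothesis has about 5% to 6% power with 30 patients, against 49% to 95% for units/kg. On the volume × titre reading power is 45% to 93% and little is lost. An open choice among four days gives about 14% to 18% false positives unadjusted and about 5% with FDR over a listed set. These figures rest on the assumed spreads, slope and residual SD above. The documents do not support a claim that the study cannot answer its question, since the data for the units/kg analysis are already planned.

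**What to change.** 1. Reconcile 1.1.2, 7.1.1, 13.1.1 and 13.2 to one primary endpoint for statistical analysis. The day-0 to day-1 change in log titre matches the primary objective; days 3, 7 and 14 become secondary. Section 7.1.2 can stay as the non-statistical primary endpoint.
2. Restate the 13.2 hypothesis with the NAb dose of 1.1.2 (log units/kg) in place of transfused volume. Units/BSA and units/plasma volume stay supportive.
3. Name one primary model: linear regression of the log-titre change on log dose/kg, with day-0 log titre as covariate and a value fixed in advance for titres below the lowest dilution. The repeated-measures and nonlinear mixed models become supportive.
4. List the tests in the FDR family, with the primary test outside it.

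A dose by baseline interaction, or a linear mixed model for the later days, is optional and not needed to cure the defect.

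The cost is wording in 7.1.1 and 13.2; no new samples or measurements are needed. There are two downsides. Later days lose co-primary status, and the day-1 slope is harder to detect if most patients start with high titres (0.17 log2 at baseline 640 against 2.64 at baseline 10 in the dilution example). If the investigators prefer another single definition, the essential step is the same: fix one endpoint, one predictor and one model before the data are examined.

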PROTOCOL TITLE: Open, non-comparative pilot study to provide access to treatment with investigational convalescent plasma and measure antibody levels in patients hospitalized with COVID-19

Given that we have a large number of clinical parameters of potential interest and a small sample of 30 patients, we do not have the statistical power or data depth for all analyses. The focus of our analysis is on the primary outcome and primary hypothesis. Much of the analyses of secondary outcomes are of the nature of exploration. We will adjust for multiplicity of comparisons (e.g. associations) using False Discovery Rate (FDR) in reporting our findings.

13.3. Sample size. A sample size determination is less plausible for this pilot study since we aim to establish the effect size of convalescent plasma transfusion on Nab titers.

However, we will conduct a post-hoc statistical power analysis to determine the actual power with the sample we obtain.

14. Provisions to Monitor the Data to Ensure the Safety of Subjects

14.1. A DSMB will be convened to include clinicians specializing in clinical trials, transfusion medicine and biostatisticians. The roster will be provided in a Modification for HRRC approval once the DSMB has been created.

14.2. The safety information that will be collected and monitored as follows: reports of rapid deterioration of respiratory or clinical status on transfusion of SARS-CoV-2 convalescent plasma and cumulative incidence of serious adverse events during the study period: febrile non-hemolytic transfusion reaction, allergic transfusion reaction, transfusion related acute lung injury (TRALI), transfusion associated circulatory overload (TACO), transfusion related infection, and hemolytic transfusion reaction.

14.3. Review of data after 10 participants have been enrolled.

14.4. Considering the novelty and rapidly changing situation of the COVID-19 pandemic, the investigators will review relevant publications that may help inform decisions related to the efficacy and safety of the investigational products.

14.5. The occurrence of any serious adverse event will be notified to the HRRC in accordance with GCP regulations. An analysis of all adverse events will be presented with the analysis of the first 10 patients enrolled and periodically thereafter.

14.6. The conditions that would trigger a suspension or termination of the research (i.e., stopping rules), are as follows:

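### Section 13.2 builds its primary hypothesis and ANOVA/ANCOVA on transfused volume, planned as 200 mL for everyone, instead of the NAb dose per kg defined in 1.1.2 and 13.1.1

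*Combined protocol and SAP*

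**What the plan says.** Section 13.2 gives the primary hypothesis as "NAb titers will increase post-transfusion in positive correlation with transfused volume of convalescent plasma when adjusted for NAb titer in the convalescent plasma". The repeated-measures ANOVA or ANCOVA is then proposed "for initial exploration of the association with the transfusion volume of convalescent plasma", with neither plasma titre nor body weight named as part of the exposure. The nonlinear mixed model in the same section names no exposure metric. A later sentence describes the exposure differently, as the "amount of convalescent plasma transfusion adjusted for NAb titer in the convalescent plasma", and says this relationship will inform standardized dosage. Section 13.2 adds: "The focus of our analysis is on the primary outcome and primary hypothesis".

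On treatment, Section 12.5.1 says: "Study subjects will receive 1 unit (200mL) of SARS-CoV-2 convalescent plasma collected from a single donor". Section 2 says it will not initially be feasible to measure titre before administration "or to adjust the volume of CP to be administered based on NAb titer in the CP or the body weight". Section 12.5 says "the total volume of plasma administration will be recorded".

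Primary objective 1.1.2 and Section 13.1.1 define the exposure as NAb dose: reciprocal plasma titre times mL, per kg body weight. Both relate it to the change from pre-treatment to day 1. Section 13.1.1 adds versions per BSA and per calculated plasma volume as comparisons. Section 2 names weight-adjusted NAb dosing as what the two earlier COVID-19 plasma studies did not examine.

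**The concern.** A regression on an exposure that does not vary by design cannot answer a dose-response question. Read literally, the model proposed for the primary hypothesis has no volume slope to estimate.

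The wording also leaves three candidate exposures: volume, volume times titre, and NAb dose per kg. Each could be called primary, and the choice could be made after the data are seen. If small incidental differences in delivered volume make a slope computable, its wide interval could be misread as absence of a dose-response. Larger differences could come from infusions stopped for a serious adverse event (Section 15.2), and those would be confounded with the reaction itself. This matters because 13.2 intends the relationship to inform later dosing.

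**Working it through.** The plan gives no figure for this association, so there is none to reproduce. From the documents: planned volume 200 mL (12.5.1), n = 30 (Section 5), NAb dose = reciprocal titre x mL / kg (1.1.2, 13.1.1).

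**Step 1. Volume exactly constant (no outside assumption).**
- Intercept + volume: the volume column is 200 times the intercept column, so rank is 1 of 2.
- Intercept + volume + plasma titre + day-0 titre: rank 3 of 4.
- Intercept + day-0 titre + either log(volume x titre) or log(dose/kg): rank 3 of 3.

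The volume coefficient has no estimate with or without covariates. The other two exposures are estimable.

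**Step 2. Delivered volume varies incidentally.** The documents give no spread. Assume a CV of 5%, which is a log2 SD of 0.0721. With four fitted parameters (30 - 4 = 26 df), the approximate 95% half-width for the slope per doubling of volume is

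t(26) x residual SD / (0.0721 x sqrt 29).

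For assumed residual SDs of 0.3, 0.6 and 1.0 log2 units this gives 1.59, 3.18 and 5.29. Doubling the volume can at most double the transfused contribution to titre, which is one log2 unit. Each of these half-widths is larger than that whole effect.

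**Step 3. Power by simulation** (n = 30, two-sided 0.05, 16 scenarios per volume CV, 4,000 replicates each). All inputs are assumptions:
- plasma titre geometric mean 320, log2 SD 1.25
- day-0 titre geometric mean 10 or 80, log2 SD 1.0 or 2.5
- assay log2 SD 0.3 or 0.6
- median weight 85 kg, ln SD 0.22; plasma volume 40 mL/kg; antibody half-life 21 days
- no endogenous rise, or a mean rise of 0.3/0.9/2.0/3.0 log2 at days 1/3/7/14 with 50% between-subject CV

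Titre at day t = (recipient titre x rise x plasma volume + plasma-unit titre x mL x decay) / (plasma volume + mL). The outcome is change in log2 titre, at day 1 or averaged over the four follow-up days as a stand-in for the repeated-measures test. Volume is adjusted for plasma titre and day-0 titre; the other two exposures are adjusted for day-0 titre.

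| Exposure | Volume CV | Power, day 1 | Power, four-day mean |
|---|---|---|---|
| Volume | 2% | 4-6% | 4-6% |
| Volume | 5% | 5-7% | 5-7% |
| Volume | 10% | 5-13% | 5-16% |
| Volume | 20% | 6-40% | 5-48% |
| Volume x titre | 0-20% | 32% to >99% | 12% to >99% |
| Dose/kg | 0-20% | 33% to >99% | 12% to >99% |

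The ranges overlap across scenarios. Within any one scenario, dose/kg exceeds volume by 28-95 points at day 1 and 5-95 points for the four-day mean. Volume without covariates, at 5% CV, has 4-6% power on either outcome.

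**Step 4. Volume x titre against dose/kg.** The two have similar power, differing by at most about 3 points in any scenario. At constant volume their log-scale correlation is sqrt(1.25² / (1.25² + (0.22/ln 2)²)) = 0.97. They are still different quantities. At an assumed titre of 1:320, every subject receives 320 x 200 = 64,000 units. Per kg that is 64,000/50 = 1,280, 64,000/85 = 753 and 64,000/130 = 492, a 2.6-fold range that volume x titre does not show.

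**The case against.** The best defence is that volume adjusted for plasma titre means volume times titre, as the later sentence in 13.2 and the unit in 13.1.1 suggest. On that reading the hypothesis is testable with almost no loss of power against dose/kg. This stands as a plausible reading, and the power loss therefore belongs only to the literal volume reading. It does not rescue the ANOVA/ANCOVA sentence, which names volume alone, and it drops the body weight that the primary objective requires.

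It can also be said that 1.1.2 and 13.1.1 already fix the exposure. They do so for the day 0 to day 1 change only. The primary endpoint for statistical analysis in 13.2 is change at days 1, 3, 7 and 14, and the only exposure its ANOVA/ANCOVA sentence names is volume.

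The ANOVA is labelled initial exploration in a 30-patient pilot that disclaims power for all analyses. It can still test whether titres rise over time without any volume term. Both points are right and limit the harm, but the hypothesised association with exposure is still not answered.

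Dosing might later vary: after the 10-patient interim, "we may consider submitting a protocol amendment requesting adjustment our patient recruitment or CP dosing". That is a possibility, not a planned source of variation.

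Finally, the power figures rest on undocumented inputs, and plasma volume simulated in proportion to weight favours dose/kg. Both are true. The simulation cannot choose between kg, BSA and plasma volume, and even dose/kg falls to 12% for the four-day mean in the worst scenario. The rank result in Step 1 depends on none of this.

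**Conclusion.** The concern holds and should be fixed. As planned, the volume effect in 13.2 is not estimable (rank 1 of 2, or 3 of 4). With incidental spread it would be estimable but close to uninformative unless the spread is large: day-1 power is at most 13% at an assumed CV of 10% and 6-40% at 20%. The rank result needs only the 200 mL plan; every power and interval figure rests on the listed assumptions. The defect is confined to the hypothesis and models in 13.2 and their conflict with 1.1.2 and 13.1.1. Objective 1.1.2 remains answerable through the day-1 analysis in 13.1.1.

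**What to change.** In the 13.2 hypothesis and the ANOVA/ANCOVA sentence, replace transfused volume with administered NAb dose as defined in 1.1.2 and 13.1.1 (reciprocal plasma titre x mL infused / kg). Do not adjust again for plasma titre. Name the same exposure in the nonlinear mixed model, which currently names none. Suggested wording: *The change in NAb titre from day 0 at days 1, 3, 7 and 14 is positively associated with administered NAb dose (units/kg).*

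State that day 1 is the contrast matching 1.1.2 and 13.1.1. Keep the per-BSA and per-plasma-volume versions as the comparisons 13.1.1 already plans, and report delivered volume descriptively. A log scale, day-0 titre as a covariate and a sensitivity analysis without incomplete infusions are optional and not needed to cure the error.

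The cost is rewording in 13.2. Plasma titre, infused volume and NAb titres at days 0, 1, 3, 7 and 14 are already planned, and weight is already needed for 13.1.1. No samples or visits are added, and the plasma given does not change.
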